LIBERATE – LIquid Biopsy Evaluation and Repository Development AT PrincEss Margaret
LFS – Li-Fraumeni Syndrome
Lynch/LS – Lynch Syndrome
MOHCCN - Marathon of Hope Cancer Centre Network
MTA - Material Transfer Agreement
MRN - Medical Record Number
NF1 – Neurofibromatosis Type 1
NPV - Negative Predictive Value
OICR - Ontario Institute for Cancer Research
PHI - Personal Health Information
PPV - Positive Predictive Value
SOP – Standard Operating Procedure
sWGS – Shallow Whole Genome Sequencing
TIDHI - Toronto Immune Digestive Health Institute
TP – Targeted Panel

Protocol Summary

CfDNA in Hereditary And High-risk Malignancies (CHARM) 2: Evaluating the Performance of a cfDNA Blood Test for Early Cancer Detection

Randomized Control Study

Sample Size

Total = 1000 patients with Hereditary Cancer Syndromes (HCS)

N = 500 (experimental arm)

N = 500 (control arm)

If other sites join our study, the appropriate MTAs and DTAs will be established, and samples collected at other institutions (who have institutional REB approval for the study) will be sent to UHN/OICR for analysis. Other sites may include: BC Cancer Agency, Mount Sinai Hospital, SickKids Hospital, Women's College Hospital, Sunnybrook Hospital, McGill Research Institute, Jewish General Hospital, IWK Health Centre, Eastern Health, Alberta University.

We will recruit up to 1000 patients at UHN.

Study Population

Our study focuses on patients with a known Hereditary Cancer Syndrome (HCS).

Accrual Period

January 2024 – December 2024

Study Design

Through the CHARM Consortium (www.charmconsortium.ca), we have shown that cell-free DNA (cfDNA) profiling can enable more frequent cancer surveillance from readily accessible blood collections and can detect cancer at the same time or earlier than clinical screening approaches. We are now conducting a prospective, multi-center, randomized control trial of cfDNA testing of 1,000 HCS carriers to 1) compare cancer detection rates with and without cfDNA testing, 2) assess cancer stage shift and clinical impact reducing mortality and morbidity cancers, and 3) assess impact of access to cfDNA results on patients' quality of life and psychological distress.

Study Duration

January 2024 – December 2031

Study Agent/ Intervention/ Procedure

cfDNA sequencing (on a blood sample), tri-annually for 4 years.

Primary Objective

Decrease the time to cancer detection and disease management in HCS carriers receiving cfDNA sequencing results compared to controls.

Secondary Objective

Use cfDNA sequencing to detect cancers that have low detection rates with standard of care surveillance methods.

Assess patient-reported outcomes and perceptions about cfDNA testing, including empowerment, distress, uncertainty, and anxiety.

Endpoints of the Study

The endpoints of this study are: 1) to assess the performance of the cfDNA assay for cancer detection in patients with HCS, including assay sensitivity, specificity, positive predictive values (PPV), and negative predictive values (NPV), 2) to assess the time to cancer diagnosis using cfDNA sequencing compared to controls, 3) to assess the detection rate of cancer with no standard of care screening available, using cfDNA sequencing, 4) assess patient reported outcomes using validated scales administered before, during, and after the study.

1.0 General Information

1.1 Study Title

CfDNA in Hereditary And High-risk Malignancies (CHARM) 2: Evaluating the Performance of a cfDNA Blood Test for Early Cancer Detection, January, 2024

2.0 Background Information

2.1 Background and Rationale

Early cancer detection is the surest path to survival, even cure. As cancer progresses, genetic changes continue to amass, thereby making late-stage cancers more aggressive, harder to eradicate, and more lethal. People who are affected by a hereditary cancer syndrome (HCS) have this lived experience, as they are born with a genetic change that puts them at high risk for developing multiple cancers throughout their lifetime. Over 200,000 Canadians harbor mutations in one of the >100 genes that cause an HCS, some facing a 100% lifetime risk of developing cancer^{1,2}. To find these cancers in time for effective treatment, all of these carriers undergo highly specific medical imaging and physical exams on a biannual or annual basis, often travelling 100s of kilometers at significant personal stress, expense, and time investment. Sadly, many of these patients receive late-stage cancer diagnoses, necessitating immediate and often radical surgeries, radiation treatments, or enrollment in experimental clinical trials.

People who carry an HCS genetic variant describe themselves as “ticking cancer time bombs” as they await the accumulation of mutations during their lifetime that trigger cancer development³. Depending on cancer type, individuals may be able to enroll in publicly-funded annual surveillance programs that are cancer-type specific and entail an array of comprehensive clinical exams and imaging modalities, such as full-body MRI, colonoscopies and mammograms. In HCS that predispose cancers for which early detection has not yet been possible, prophylactic surgeries are recommended, such as removal of breasts, ovaries, and fallopian tubes for carriers of Hereditary Breast and Ovarian Cancer (HBOC), removal of uterus and ovaries in Lynch Syndrome (LS), and gastrectomy for carriers of Hereditary Diffuse Gastric Cancer (HDGC)^{4,5,6}. These life-altering surgeries place a heavy psychological and physical burden on patients, particularly those of childbearing age who face uncertain timing of growing a family versus potential development of a cancer.

Canadians with HCS face multiple challenges, primary among them being inequitable access to clinical screening programs. An HCS patient's children and other first-degree relatives each have a 50% chance of inheriting the same causal gene variant; timely screening and intervention can save their lives. Unfortunately, follow-up of at-risk family members is often inadequate or omitted entirely, in part due to complex referral criteria and provincial differences in screening recommendations. Additionally, people living in rural, remote and/or northern areas of Canada are isolated from the specialized genetics and oncology clinics that are typically only available in urban locations. Therefore, a paradigm shift is needed from the current fragmented approach to individual HCS towards a new, forward-thinking approach that utilizes a single, highly quantitative platform effective across all types of hereditary cancers.

A promising new technology for early cancer detection involves sequencing of the cell-free DNA (cfDNA), shed into the circulation by mostly healthy cells. Cancer cells can also shed DNA into the circulation, which can be distinguished from those shed by healthy cells. As access to high-risk screening is not available to all, cfDNA analysis from a simple blood test may provide a more accessible alternative method^{7,8,9}. A blood test is minimally invasive and would require minimal infrastructure to deliver.

Our community, known as the CHARM Consortium (cfDNA in Hereditary And High-Risk Malignancies), was founded in 2018 to address HCS knowledge and delivery gaps through evaluation of blood-based cfDNA testing. Comprised of 8 genetics clinics from 5 Canadian provinces, CHARM is a patient-engaged biobanking and clinical data annotation service, where blood and available tumour samples are collected from HCS carriers at annual screening visits. Analysis of these samples has led to new advancements in cfDNA sequencing that we propose to test with this prospective trial, by evaluating the detection rate of cfDNA sequencing and the clinical benefit gained by following up on detection of early cancer using cfDNA. Specifically, we have demonstrated the use of three technologies to detect early cancer in HCS through analysis of cfDNA in blood plasma: 1) the CHARM gene panel, a targeted sequencing approach that provides in-depth mutational data on a core set of genes frequently mutated in FCS tumours and offered clinically by our program, 2) cell-free methylated DNA immunoprecipitation and high-throughput sequencing (cfMeDIP-seq), which can detect the specific organ from which the cancer-triggering DNA changes arise, and 3) shallow whole genome sequencing (sWGS), which detects accumulated mutations, copy number alterations and DNA fragmentation patterns that occur secondary to the inherited mutation. These results have suggested that integration of mutation, copy number, and functional (methylation or fragmentation) aspects of cfDNA provide the greatest sensitivity for early HCS detection.

In this study, we will enroll 1,000 patients from across Canada's HCS screening programs. Half of the patients will be randomized to have cfDNA analysis with results returned to managing physicians who will follow-up any abnormal cfDNA findings with appropriate clinical imaging and heightened surveillance. At the end of this study, the rate of cancer detection using cfDNA-informed surveillance will be compared with the rate of detection in the cohort of patients who did not receive the result of the cfDNA test but were managed according to current conventional screening programs.

2.4 Study Population

The study population will include patients with a confirmed genetic diagnosis of HBOC, LS, NF1, LFS, PALB2 and HDGC, and who are receiving standard-of-care clinical assessment for cancer by a managing physician under a provincial screening program or cancer surveillance protocol.

3.0 Study Objectives and Hypothesis

3.1 Study Objectives

3.1.1 Primary Objective

Our primary study objective is to establish whether blood plasma cfDNA testing can detect cancers at the same time as, or earlier, than conventional standard-of-care screening tests for carriers of HCS. We will also assess the time to disease management in carriers receiving cfDNA sequencing results compared to controls.

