4.1 Overall Study Design

We are conducting a randomized control trial to assess the use of cfDNA analysis in cancer surveillance protocols for patients with HCS. We will recruit 1,000 patients across Canada with a known/suspected genetic diagnosis of one of the following HCS: HBOC, LS, NF1, LFS, PALB2, or HDGC that are receiving standard-of-care clinical assessment for cancer by a managing physician under a provincial screening program or cancer surveillance protocol.

The study design is illustrated in Figure 1. At study enrollment, participants will be randomized to a control cohort (n=500) or an experimental cohort (n=500), stratifying for genetic HCS background. All participants in the experimental cohort will provide blood samples tri-annually (every four months) for four years, either at the study hospital, or at a local blood laboratory (e.g., LifeLabs or Dynacare). Whenever possible, patients will have research blood collected at the same time as routine blood collections for clinical purposes, to avoid additional venipunctures. Participants randomized to the control cohort will have the option to donate samples to the CHARM Consortium Biobank, for use in future research. Participants in the control cohort can donate between 1-3 blood samples a year, for the duration of the study.

Participants in both the control and experimental cohorts will continue to receive standard-of-care cancer surveillance according to current guidelines, as they were prior to study enrollment. Blood samples from the experimental cohort will be subject to a

Figure 1. Study Design.

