cfDNA sequencing assay, and results will be communicated to participants by the study team. Participants who receive a “positive” cfDNA assay result will be offered follow-up diagnostic procedures to confirm or rule out the presence of a malignancy. The diagnostic investigations are outlined in “Cohort Specific Diagnostic Workflows”, appended to this protocol. If an abnormality is identified by a diagnostic investigation done in follow-up to a “positive” cfDNA assay result, additional investigations (e.g., imaging or biopsy) will be performed as part of the participants clinical care, and will be guided by the participant’s clinical team, or study investigator. All participants will be followed by the study team for a minimum of 5 years, from their first blood collection. To assess the efficacy of the cfDNA assay, we will compare cfDNA assay results to the results of the participants standard of care cancer surveillance results.

Lastly, we will use questionnaires and semi-structured interviews to explore participants’ experiences with cfDNA testing, to understand perceptions of the clinical utility of cfDNA tests for HCS management and identify factors facilitating or impeding the uptake of this test in HCS management and patient decision making.

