4.11 Endpoints

The endpoints of this study are:

1. To assess the performance of the cfDNA assay for cancer detection in patients with HCS, including assay sensitivity, specificity, PPV, and NPV. The test performance endpoint is a diagnosis of cancer and will be assessed at multiple points during the study (at a minimum yearly). Cancer diagnosis will be confirmed by imaging, pathology, or other confirmation deemed appropriate by the treating physician.
2. To assess the time to cancer diagnosis using cfDNA sequencing compared to controls.
3. To assess the detection rate of cancer with no standard-of-care screening available (e.g., pancreatic cancer, endometrial cancer) using cfDNA sequencing.
4. To assess patient reported outcomes (including anxiety, empowerment, distress, risk perception) using validated scales administered before, during, and after the study.

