4.13.2 Potential Benefits

Some participants will receive a “positive” cfDNA assay result, and the follow-up investigations may lead to a diagnosis of cancer, which can then be treated appropriately. The cancer diagnosis may happen earlier than if the participant were not involved in the study, and only partaking in standard-of-care surveillance.

This study will help evaluate the feasibility and acceptability of implementing cfDNA sequencing as part of standard-of-care surveillance for high risk patients. Should this study show benefits for detection of cancer in HCS patients comparable to current surveillance protocols, this may have broader implications for HCS families across Canada.

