8.0 Statistics

We will compare the cancer detection rate between control and experimental cohorts. Analysis will be stratified by the type of the tumours detected within each HCS, as well as across the entire cohort. Between the cohorts, we will first compare the cancers detected to ascertain whether cfDNA testing results in a more sensitive detection of clinically confirmed cancers, as well as calculate negative and positive predictive values of cfDNA findings as confirmed by clinical testing (MRI, ultrasound, biopsy, protein biomarkers, etc.). This analysis will also ascertain whether cfDNA is more or less effective at detecting specific cancer types compared to standard-of-care screening alone.

We will also conduct comparisons that compare categorical (e.g. cancer stage) and continuous time course data (e.g. time to symptom development, time to treatment, and time on treatment). The first comparison is a stage shift analysis, whereby we will assess whether cancers are being detected at earlier stages using cfDNA versus screening results from the same programs. Categorical variables of stages I-IV within each cancer type as defined by NCCN criteria will be compared using Pearson's χ^2 test. Binary comparison of “early” and “late” stage across all cancer types will be performed using Fisher Exact test. The second comparison will be calculation of the time to first treatment relative to the date of the last annual clinical screening visit. This comparison of continuous variables using the t-test will establish whether triannual cfDNA testing accelerates off-cycle clinical follow-up and medical treatment compared to waiting for annual clinic visits. The third comparison will compare mortality and morbidity specifically for pancreas, esophagus, brain, lung, and stomach cancers. We will calculate the time between detection of a cancer and when patient manifest symptoms of cancer (morbidity 1), how long patients are afflicted with cancer symptoms after detection and during treatment (morbidity 2), and how long a patient undergoes treatment before succumbing to disease (mortality) or, in the case of effective treatments, the time until treatment is discontinued, or patients transition to the outpatient setting. Continuous variables will be compared by t-test.

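### The primary question is put three ways, and its same-time-or-earlier form cannot be answered by comparing two arms that both keep standard screening

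*Protocol*

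**What the plan says.** The protocol states its primary question in three places.

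- Protocol Summary, Primary Objective: "Decrease the time to cancer detection and disease management in HCS carriers receiving cfDNA sequencing results compared to controls".
- Section 3.1.1: to establish whether "cfDNA testing can detect cancers at the same time as, or earlier, than conventional standard-of-care screening tests". A second sentence adds time to disease management, relative to controls.
- Section 8.0: power rests on improved cancer detection, called the primary outcome there. The rates run from 5% without cfDNA up to 10% with it. Power above 97% is claimed for a gain of at least 2% with 1,000 patients, two-sided 0.05. Section 3.1.2 lists more frequent cancer detection as a secondary objective.

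The design is an add-on. Section 4.1: "participants will be randomized to a control cohort (n=500) or an experimental cohort (n=500), stratifying for genetic HCS background", and "Participants in both the control and experimental cohorts will continue to receive standard-of-care cancer surveillance according to current guidelines". Section 6.0 repeats that all participants continue standard screening.

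Two kinds of comparison are planned. Between arms, endpoint 2 in Section 4.11 is "To assess the time to cancer diagnosis using cfDNA sequencing compared to controls", and Section 8.0 says its analysis will show "whether cfDNA is more or less effective at detecting specific cancer types compared to standard-of-care screening alone". Within participants, Section 4.1 says "we will compare cfDNA assay results to the results of the participants standard of care cancer surveillance results", and Section 7.0 adds a yearly percentage of screening-found cancers that the assay missed. No margin is given for detection at the same time.

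**The concern.** The three statements differ in outcome (time or rate), in comparison (assay against screening tests, or arm against arm) and in direction (better, or no worse). Only the Section 3.1.1 wording can be satisfied by equality. Because standard screening continues in both arms, equality between arms says nothing about whether the assay detects cancer.

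At stake is what a null trial may conclude. If the objective is read at arm level, a non-significant difference could be described as cfDNA detecting cancers at the same time as standard screening. This design does not test whether cfDNA matches, or could stand in for, that screening. A statistical analysis plan cannot settle this alone, because it would have to choose between conflicting primary objectives in the protocol.

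**Working it through.** **1. The three statements side by side**

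- Summary: arm against arm; time to detection and management; shorter. Equal arms answer no.
- Section 3.1.1: assay against screening tests; timing; same or earlier. If judged between arms, equal arms answer yes.
- Section 8.0: arm against arm; diagnosis rate; higher. Equal arms answer no.

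**2. What the randomised contrast measures**

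For one cancer, let S be the date on which standard screening would find it, and C the date on which a cfDNA-triggered work-up would find it (C is infinite if the assay never signals).

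- Control arm: detection at S.
- Experimental arm: detection at min(S, C).

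If C = S, the experimental date is S. If C is infinite, it is also S. An assay that matches screening exactly and one that never detects anything therefore give the same arm-level data. The contrast identifies only the gain when C < S. This assumes that results do not change attendance at standard screening and that work-ups after false positives find no cancer by chance.

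**3. What the within-participant comparison measures**

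- Standard screening finds the cancer: S is observed and the assay results up to that date are known, so missed and concurrent signals can be counted.
- A cfDNA-triggered work-up finds it first: C is observed, but S is never observed. The lead time S − C is missing for exactly the cancers that cfDNA finds early.

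**4. The protocol's own power figure, and what a null result means**

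Inputs from Section 8.0 and Section 4.1: 5% versus 7% (a gain of 2 points), 500 per arm, two-sided 0.05.

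Power = Φ[(d − 1.96·SE0)/SE1], with d = 0.02:

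- SE0 = √(2 × 0.06 × 0.94/500) = 0.01502
- SE1 = √((0.05 × 0.95 + 0.07 × 0.93)/500) = 0.01501
- Power = Φ[(0.02 − 0.02944)/0.01501] = Φ(−0.63) = 26.5%

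The stated figure of over 97% is not reproduced. It would need about 4,157 per arm. For 5% versus 10% the same formula gives 85.2%. That discrepancy is a separate matter. Here it matters because a real 2-point gain would be non-significant in 100 − 26.5 = 73.5% of trials, so a null arm comparison does not separate a useless assay from a modestly useful one.

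**5. An assay that adds nothing**

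The protocol gives no time distribution, so diagnosis rates are used: 5% in both arms, 500 per arm, exact enumeration of the pooled z-test.

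- Significant in favour of cfDNA: 2.4%.
- Not significantly worse than control: 97.6%. This would be a success rate only if not being significantly worse counted as success, a rule that the protocol does not state.

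**6. Would a margin repair the arm-level reading?**

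Assume 5% in both arms and one-sided 0.025: power = Φ(m/√(2 × 0.05 × 0.95/500) − 1.96), with standard error 0.01378. For assumed margins of 2, 3 and 4 points, an assay that adds nothing passes with probability 31%, 59% and 83%. The true difference is zero, so such an assay is truly non-inferior. A margin would test whether adding cfDNA does harm to detection, not whether cfDNA detects cancer.

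**The case against.** A reader might infer that the protocol is set up so that a worthless assay almost always appears to succeed. The documents do not support that.

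- Section 3.1.1 asks whether cfDNA can do this; it does not assert that it can. Its first sentence compares a test with tests, and only the second turns to controls.
- No section makes equality between arms, or a result not significantly later, a success. The stated inferential frame is a two-sided 0.05 test for an increased diagnosis rate, and the hypothesis in Section 3.2 is directional. The 97.6% in the working belongs to a rule the protocol does not contain.
- The test-level analyses (Section 4.1, endpoint 1 in Section 4.11, Section 7.0) would expose an assay that misses cancers found by standard screening. Section 7.0 gives 50% missed as an example of underperformance.
- Endpoint 2 estimates the acceleration at group level, so lead time is not wholly out of reach.
- In Section 8.0, the comparison with standard screening alone follows a reference to the cohorts and can be read as a legitimate add-on contrast. The phrase "benefits for detection of cancer in HCS patients comparable to current surveillance protocols" in Section 4.13.2 is benefits prose, not an analysis rule, and the sentence before it speaks of cfDNA as part of standard surveillance.
- Participants are told to keep up standard screening, and compliance is monitored.

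All of this stands, and it rules out the stronger reading. It does not reconcile the three statements of the primary question, make equality between arms informative, or supply the unobserved screening date for cancers found first through cfDNA.

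**Conclusion.** The point holds as an inconsistency in the primary objective. Section 3.1.1, the Protocol Summary and Section 8.0 ask different primary questions, and the Section 3.1.1 version is uninformative if judged by the randomised contrast, because an assay that adds nothing and an assay that equals screening give the same arm-level data. Within-participant comparisons can show what the assay misses, but not how much earlier it is for cancers found through a cfDNA-triggered work-up.

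The size lies in interpretation. At 500 per arm, a true 5% versus 7% rate is non-significant about 73.5% of the time, so a null result would be likely even for an assay with a real 2-point benefit. This uses the protocol's rates and a simple two-proportion test. The structural argument needs no figures, only the assumptions on attendance and chance findings given in the working.

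**What to change.** - Reword Section 3.1.1 as one between-arm superiority objective in line with the Protocol Summary: adding cfDNA results to standard-of-care screening shortens time to cancer detection compared with standard-of-care screening alone. Remove the same-time alternative from the arm-level objective.
- Make the primary outcome and power statement in Section 8.0 match that objective, and settle the place of the diagnosis rate, which is primary there and secondary in Section 3.1.2.
- Keep assay concordance, sensitivity and the other endpoint 1 measures as a separate test-level objective.
- Limit the effectiveness statement in Section 8.0 to the effect of adding cfDNA.
- State that a non-significant arm difference is not evidence that cfDNA is equivalent to, or can replace, standard screening.

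The cost is protocol wording, a restated power calculation and a narrower claim: add-on benefit only. As a rough guide, suppose hazards are proportional with a ratio close to the ratio of the stated rates. At 5% versus 7%, 25 + 35 = 60 events and a hazard ratio of 1.4 give Φ(√60/2 × ln 1.4 − 1.96) = 25.6% power. At 5% versus 10%, 25 + 50 = 75 events and a ratio of 2.0 give 85.1%. These are close to the 26.5% and 85.2% for rates, so on these assumptions moving to a time outcome loses little power.
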